**Official Title of the study: Effects of Intermittent Fasting in Metabolic Dysfunction Associated Fatty Liver Disease**

**NCT number: NCT06664684**

**Date of the document: 06.05.2022**

**Study Protocol**

***Patients***

This study was approved by the Ethics Committee of Marmara University School of Medicine (No: 09.2022.707) Informed consent was obtained from each patient included in the study. This is a prospective non-drug intervention study conducted by the same gastroenterologist on patients diagnosed with MAFLD. Individuals with fatty liver disease diagnosed by vibration-controlled transient elastography are diagnosed with MAFLD if at least one of the following three conditions is present: overweight/obesity, type 2 diabetes mellitus (T2DM), or underweight or normal weight with at least two metabolic risk abnormalities [waist circumference, blood pressure, triglycerides, high-density lipoprotein cholesterol (HDL-C), prediabetes, insulin resistance, high-sensitivity C reactive protein (CRP)]. All of our patients were diagnosed with MAFLD because their BMI was above 25 kg/m^2 in addition to the detection of fatty liver.

Exclusion criteria were patients with an average daily alcohol consumption of >20 g for females and >30 g for males; pregnant or lactating women; patients with ischemic heart disease or heart failure, chronic inflammatory diseases, chronic viral infections, cancer, moderate-to-severe kidney disease, uncontrolled hypertension, and eating disorders; those with a history of bariatric surgery; and those on insulin due to increased risk of hypoglycemia.

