***Design***

Patients who voluntarily agreed to participate in the study were randomly assigned into two groups. Patients enrolled in the study were referred for an initial consultation with a dietitian following their diagnosis by a gastroenterologist. The energy-restricted diet group followed an energy-restricted diet for 8 weeks, while the energy + time-restricted diet group followed the same diet and a 16:8 eating pattern and restricted food intake to an 8 h window each day. The effectiveness of the intervention was assessed using anthropometric and biochemical measurements, and Fibroscan investigations were performed before the intervention (T0) and after the intervention (T8).

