***Measurements***

Blood samples were collected from patients after 12 h of fasting. The samples were centrifuged for 15 min and stored at -80 °C after serum separation until analysis. Serum FGF-21, Beclin-1, and ATG-5 were analyzed using enzyme-linked

immunosorbent assay (ELISA) kits, following the manufacturer's protocols (Human FGF-21 ELISA, Biovendor, Brno, Czech Republic; Human BECN1 [Beclin-1] ELISA Kit, ElabScience, Houston, TX, USA; Human Autophagy protein 5 [ATG5] ELISA Kit, MyBioSource, Inc., San Diego, USA) and in duplicate.

- The extent of hepatic steatosis and fibrosis was determined using transient elastography on a Fibroscan 502 TouchR device(Echosens SA, Paris, France). All Fibroscan measurements were performed following the manufacturer's instructions as specified previously.
- Patients' heights were measured using a stadiometer (Seca 769), barefoot, feet side by side, and head in the Frankfort plane. Body composition was determined using the bioelectrical impedance method (Tanita MC 780 P).

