Official Title of the study: Effects of Intermittent Fasting in Metabolic Dysfunction Associated Fatty Liver Disease

NCT number: NCT06664684

Date of the document: 06.05.2022

Statistical Analysis Plan

Study data were analyzed using SPSS 28.0 software suit. Statistical significance was set at $p < 0.05$ for all analyses. Data were checked for normality of distribution using the Kolmogorov–Smirnov test. Categorical variables were analyzed using the chi-square test. Median (Quartile 1–Quartile 3) values were used in descriptive statistics. The Mann–Whitney U test was used to determine whether the baseline values were similar between the two groups before the intervention. The before/after comparison of the quantitative data was performed using the Wilcoxon test.

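### If the qualifying elastography scan also serves as T0, the within-arm Wilcoxon test cannot separate regression to the mean in steatosis from a diet effect

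*Protocol*

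**What the plan says.** Entry (Protocol, Patients): "Individuals with fatty liver disease diagnosed by vibration-controlled transient elastography are diagnosed with MAFLD", given at least one further metabolic condition. The section adds that every patient met the definition through a BMI above 25 kg/m², "in addition to the detection of fatty liver". So all patients passed an elastography finding of steatosis. No cut-off is given.

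Outcome (Protocol, Measurements): "The extent of hepatic steatosis and fibrosis was determined using transient elastography on a Fibroscan 502 TouchR device". Timing (Protocol, Design): "Fibroscan investigations were performed before the intervention (T0) and after the intervention (T8".

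Sequence (Protocol, Design): patients were "referred for an initial consultation with a dietitian following their diagnosis by a gastroenterologist". No second pre-treatment scan is described.

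Arms (Protocol, Design): patients "were randomly assigned into two groups". "The energy-restricted diet group followed an energy-restricted diet for 8 weeks"; the other arm followed the same diet plus a daily 8-hour eating window. Neither arm is untreated.

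Analysis (SAP): "The before/after comparison of the quantitative data was performed using the Wilcoxon test". The Mann–Whitney test is assigned to baseline values only. No between-arm test of T8 values or of change in quantitative data is stated.

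**The concern.** Selection and outcome use the same measurement. A patient whose true steatosis is near the threshold enters if measurement error pushes the qualifying reading up, and is screened out if error pushes it down. Among those admitted, the qualifying reading is therefore too high on average. The T8 reading is not selected in this way. If the qualifying reading is also the T0 value, the expected T0–T8 change is a fall even when neither diet does anything.

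T0 is tied only to preceding the diet, and the diagnostic scan meets that condition. With no untreated arm and only a within-arm test of change, the stated analysis has nothing to set such a fall against. At stake is a significant fall in steatosis in one or both arms being reported as evidence that the diet works.

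**Working it through.** The plan gives no sample size, cut-off, SD or scan repeatability, so there is no figure of its own to reproduce. The check asks how large the artefact could be if the qualifying scan is T0.

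Model. Scale readings in the screened population to mean 0 and SD 1. Let c be the entry cut-off in SD units and ρ the test-retest correlation, with independent errors between scans and no true change.

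- Mean qualifying reading of those admitted: λ = φ(c) / (1 − Φ(c)).
- Their expected T8 reading: ρλ.
- Expected spurious fall: (1 − ρ)λ.

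Inputs, all assumed: 30% to 90% of those screened qualify, ρ from 0.7 to 0.9, and 10 to 50 patients per arm. The test is taken as two-sided; p < 0.05 is from the SAP.

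Results for three settings, with Wilcoxon rejection rates from simulation (1,000 runs per setting, no diet effect):

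| Share qualifying | c | λ | ρ | Fall = (1 − ρ)λ | Rejects, 20 per arm | Rejects, 50 per arm |
|---|---|---|---|---|---|---|
| 90% | −1.28 | 0.1755/0.9 = 0.195 | 0.9 | 0.1 × 0.195 = 0.02 SD | 5.4% | 5.9% |
| 50% | 0 | 0.3989/0.5 = 0.798 | 0.8 | 0.2 × 0.798 = 0.16 SD | 18.5% | 40.8% |
| 30% | 0.52 | 0.3477/0.3 = 1.159 | 0.7 | 0.3 × 1.159 = 0.35 SD | 51.3% | 88.7% |

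For a sense of scale only, take an SD of 50 dB/m. Neither that figure nor the unit is in the documents. λ × SD is then:

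- 22.0 dB/m for a screened mean of 280 and cut-off 248;
- 38.6 for mean 250 and cut-off 248;
- 57.1 for mean 250 and cut-off 275.

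Multiplying by 1 − ρ, from 0.1 to 0.3, gives falls of 2.2–6.6, 3.9–11.6 and 5.7–17.1 dB/m. In SD units these run from 2.2/50 = 0.04 to 17.1/50 = 0.34, inside the range of the table. They leave out the near-null setting in its first row.

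Two alternatives were simulated over all the combinations, at 20 per arm:

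- T0 taken as a separate scan after qualification: expected fall 0; Wilcoxon rejection 3.6–6.2%.
- Qualifying scan kept as T0, with change compared between arms by Mann–Whitney: rejection 3.5–5.2%.

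The simulation standard error at 5% is √(0.05 × 0.95/1000) = 0.7 percentage points, so both are compatible with the nominal 5%. In the second case the artefact has the same expectation in each randomised arm and cancels.

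**The case against.** The strongest objection is that reuse of the scan is nowhere stated. The Design section lists Fibroscan with the anthropometric and biochemical assessments at T0 and T8, which reads naturally as a set of study visits, and it places a dietitian referral between diagnosis and diet. This stands. A reader might infer that the trial did use the diagnostic scan as T0, or that any fall in steatosis is spurious. The documents support neither. They leave the link open, and in the model above a separate T0 scan removes the artefact.

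The size is equally open. If nearly all screened patients sat well above the threshold, the fall is negligible and the error rate is close to nominal. A reader might take the dB/m figures as an estimate for this trial; they are illustrations from outside inputs.

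A reader might also infer that the comparison of the two diets is biased. It is not: the arms differ only in the eating window, and the artefact cancels from that contrast. Nor is an effect shown for fibrosis, weight or the biomarkers, which would be affected only as far as their errors correlate with the qualifying reading.

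Finally, a within-arm fall could not be credited to diet in any case, because time trends and trial participation are also uncontrolled. That is correct, and the remedy overlaps with the wider lack of a between-arm test. What is particular here is a bias with a known direction, towards benefit, on the variable used for entry.

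**Conclusion.** The point holds as a conditional one. Entry and outcome share a method, nothing establishes that T0 is independent of the qualifying scan, and the one stated test of change is within arm. If the qualifying scan is T0, a fall in the measured reading is expected in both arms without any change in liver fat, and the stated analysis cannot distinguish it from benefit.

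Under the assumed inputs the fall is between about 0.02 and 0.35 SD. At 20 per arm the corresponding false-positive rate per arm runs from about 5% to about 51%. These figures rest on normal readings, independent errors and assumed qualifying shares, correlations and arm sizes, none of which the documents supply. The threat is to within-arm claims about steatosis; the randomised contrast is not biased by it.

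**What to change.** Amend the SAP so that conclusions on steatosis rest on the between-arm comparison of T0–T8 change, or of T8 adjusted for T0. Report the within-arm Wilcoxon results as descriptive, not as evidence of a diet effect. This protects the conclusion whichever scan was T0. It answers what the eating window adds; with both arms on the energy-restricted diet, no comparison in this design isolates the effect of that diet itself.

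Report whether T0 was the qualifying scan. If a separate pre-intervention scan exists for every patient, use it as T0 for all. If it exists only for some, keep one definition throughout, so that T0 does not mean different things within an arm.

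The cost is one added SAP analysis on readings the plan already collects, and a less favourable within-arm claim. No new scan is needed.

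### With no drug- or weight-stability rule and no record of drug changes, the planned before/after test cannot separate the diet from other causes of 8-week change

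*Protocol*

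**What the plan says.** **Eligibility (Protocol, Patients).** The exclusion list closes with "those with a history of bariatric surgery; and those on insulin due to increased risk of hypoglycemia". Insulin is the only drug in the list, and hypoglycaemia is the stated reason. The item closest to a stability rule is in the group "moderate-to-severe kidney disease, uncontrolled hypertension, and eating disorders". It screens out one poorly controlled condition but asks nothing about recent drug starts or recent weight change.

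Type 2 diabetes appears in the general disease definition: "overweight/obesity, type 2 diabetes mellitus (T2DM), or underweight or normal weight with at least two metabolic risk abnormalities". The same section says every patient qualified on a BMI above 25 kg/m². Diabetes is therefore neither required nor excluded, and a patient with diabetes who is not on insulin can enter.

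**Allocation and timing (Protocol, Design).** "Patients who voluntarily agreed to participate in the study were randomly assigned into two groups". Both arms receive the same energy restriction; "the energy + time-restricted diet group followed the same diet and a 16:8 eating pattern". On timing, "Patients enrolled in the study were referred for an initial consultation with a dietitian following their diagnosis by a gastroenterologist". That gives an order of events but no interval. The assessments named for T0 and T8 are anthropometric, biochemical and Fibroscan. No medication or weight history is listed.

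**Analysis (SAP).** Quantitative outcomes are compared before and after with a Wilcoxon test. The Mann–Whitney test is described for baseline values only. A chi-square test is named for categorical variables, with no time point. The significance threshold is 0.05.

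**The concern.** Three omissions act together. A patient who started a non-insulin glucose-lowering, weight-lowering or lipid-lowering drug shortly before T0, or who was already losing weight, is eligible. Nothing in the listed assessments would identify that patient afterwards. And the one 8-week test described for quantitative outcomes measures total change from T0 to T8, whatever its cause.

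Weight, body composition, biochemistry and liver fat can all respond to such drugs and to weight loss under way. A significant before/after result could then be read as a diet effect when part or all of it has another source. If each arm is tested separately, there is a second risk: one arm may reach significance and the other not, and the difference may be credited to the eating window.

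**Working it through.** **Plan's own figures.** The documents give no sample size, effect size or standard deviation, so there is nothing to reproduce. Everything below is illustration on assumed inputs.

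**1. Shift in the within-arm mean.** Assume a share p = 15% of patients start or change a relevant drug, with an effect d = 3 kg over 8 weeks.
- Shift = p × d = 0.15 × 3 = 0.45 kg with no diet effect.
- It is proportional to each input: halving one gives 0.225 kg, doubling one gives 0.90 kg.

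**2. The same shift in standard deviation (SD) units.** Assume the SD of weight change is otherwise 2 to 4 kg.
- Added variance = d² × p(1 − p) = 9 × 0.15 × 0.85 = 1.15 kg².
- Total SD = √(4 + 1.15) = 2.27 kg, or √(16 + 1.15) = 4.14 kg.
- Shift = 0.45/2.27 = 0.20 SD, or 0.45/4.14 = 0.11 SD.

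**3. Effect on the planned test.** Simulation with 2,000 runs per setting, normally distributed change scores, two-sided 0.05, 15, 20 or 30 patients per arm, no diet effect, and the same background shift in both arms. Ranges run over the three arm sizes.

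| Background shift | Within-arm Wilcoxon significant | One arm significant, the other not | Between-arm Mann–Whitney on change |
|---|---|---|---|
| 0 | 4–5% | 8–11% | 4–5% |
| 0.2 SD | 10–18% | 17–28% | 5% |
| 0.3 SD | 17–33% | 29–45% | 4–5% |
| 0.5 SD | 41–74% | 38–51% | 4–5% |

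Simulation error near 5% is √(0.05 × 0.95/2000) ≈ 0.5 percentage points. The inputs in step 1 reach at most the 0.2 SD row. The 0.5 SD row would need a mean shift of 0.5 × 2.27 = 1.13 kg or more.

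**4. Cost to a between-arm comparison when the cause is unrelated to arm.**
- SD of the between-arm difference in the affected share = √(2 × 0.15 × 0.85/n) = 0.113 at n = 20 per arm and 0.071 at n = 50.
- Multiplied by 3 kg, this is 0.34 and 0.21 kg. It is noise centred on zero.
- The standard error grows by a factor of 2.27/2 = 1.13 or 4.14/4 = 1.04, that is by 13% to 4%.

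**5. If the shift occurs in one arm only after randomisation.** The between-arm test is then significant in 8–12% of runs at 0.2 SD, 10–19% at 0.3 SD and 26–46% at 0.5 SD, again with no diet effect.

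**The case against.** **Randomisation already deals with this.** It largely does for anything that precedes T0. Patients are randomised and share the same base diet, so earlier drug starts and existing weight loss are balanced in expectation. Chance imbalance is ordinary sampling variation, which a valid between-arm test already allows for. This stands, and it limits the point. It does not rescue the SAP, which describes no between-arm test of change.

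**A before/after test fails even if every patient is stable.** True: regression to the mean and study participation would remain. The missing between-arm comparison is the larger defect, and a stability rule without it would be a partial remedy.

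**Stronger readings.** A reader might infer from the referral sentence that patients were newly diagnosed, began the diet at diagnosis and began other treatment at the same time. The documents do not say so. They give no interval between diagnosis and diet and report no other treatment. A reader might also infer that many patients had diabetes; the number is not given, and all qualified on BMI. Finally, a reader might infer that the between-arm contrast is biased. Only drug changes after randomisation that differ by arm could do that. Patients know whether they follow a 16:8 pattern, so it is possible, but nothing in the documents shows that it happened.

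**Feasibility.** Both documents are written in the past tense. If enrolment had ended, an eligibility rule could no longer be applied, though the analysis and reporting changes still could.

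**Conclusion.** The point holds in a limited form. No stability requirement or drug-change record is described, so the before/after Wilcoxon test cannot separate the diet from recent or concurrent drug starts or from weight loss already under way. For a between-arm comparison, causes that precede T0 add noise rather than bias.

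The likely size is modest. The illustrative inputs raise the within-arm false-positive rate from about 4–5% to, at most, roughly 10–18% for weight, and widen the between-arm standard error by 4–13%. These figures rest on the assumed 15%, 3 kg, SD of 2 to 4 kg and arm sizes, none of which the documents supply. The conclusion about attribution does not depend on them. It follows from the eligibility list, the listed assessments and the choice of test.

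**What to change.** 1. **Eligibility.** Exclude patients who started or changed a glucose-, weight- or lipid-lowering drug, or had clear intentional weight loss, in a fixed period before T0. Three months is an example; the sponsor should justify the length chosen. This governs entry only and does not restrict the treatment any patient may receive.
2. **Record.** Note such drugs and recent weight history at T0 and any start or change of these drugs by T8, and report them by arm.
3. **Analysis.** Make the T0–T8 change compared between the randomised arms the main comparison, with all randomised patients kept. A Mann–Whitney test on the change would fit the SAP's existing methods. It estimates what the 16:8 pattern adds to the shared diet. Within-arm change should be descriptive, since no arm goes without the diet.
4. **Exploratory only.** Any analysis that leaves out patients whose drugs changed after T0 conditions on a post-randomisation event and can itself introduce bias if those changes depend on arm.

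**Cost.** One eligibility line, a short history at the existing first consultation and at T8, and a between-arm test. A few patients become ineligible or enter later. If enrolment was already complete, item 1 falls away and item 2 depends on what clinical records can supply.

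### The hypoglycaemia exclusion names insulin only, so patients on other drugs that can cause hypoglycaemia remain eligible for energy restriction plus a daily 16 h fast

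*Protocol*

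**What the plan says.** The Protocol's Patients section ends its exclusion list with "those on insulin due to increased risk of hypoglycemia". This is the only exclusion tied to hypoglycaemia and the only one that names a drug treatment.

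The same section defines MAFLD as fatty liver plus at least one of "overweight/obesity, type 2 diabetes mellitus (T2DM), or underweight or normal weight with at least two metabolic risk abnormalities". It then reports how enrolled patients qualified: "All of our patients were diagnosed with MAFLD because their BMI was above 25" kg/m². Type 2 diabetes does not appear among the exclusions.

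The Design section assigns patients at random to an energy-restricted diet for 8 weeks or to a combined arm that "followed the same diet and a 16:8 eating pattern and restricted food intake to an 8 h window each day".

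The SAP says nothing on eligibility or safety.

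**The concern.** The reason given for excluding insulin users is the risk, not the drug. By that reasoning the criterion should cover every treatment that carries the risk to a relevant degree, yet it covers one. Sulfonylureas and glinides are the obvious omissions, because they can lower glucose too far when food intake drops or meals are spaced out. Both arms reduce intake, and one also lengthens the daily gap between meals.

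What is at stake is an avoidable hazard to individual patients, of a kind the Protocol itself treats as grounds for exclusion. The concern is not about the estimate of any treatment effect.

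**Working it through.** The documents give no figure to reproduce here. The check is a reading of the eligibility rule against the intervention, with a short calculation to describe the exposure.

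**Step 1. Can a patient with type 2 diabetes enter?** Yes. Diabetes is one of the three conditions that establish MAFLD, and it is not excluded. That all enrolled patients qualified through BMI does not rule out diabetes alongside it. The insulin exclusion also suggests that treated diabetes was expected among candidates.

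**Step 2. Does any listed exclusion remove such a patient who takes a sulfonylurea or glinide?** The list covers:

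- alcohol intake above set limits
- pregnancy or breastfeeding
- ischaemic heart disease and heart failure
- chronic inflammatory disease and chronic viral infection
- cancer
- kidney disease of at least moderate degree
- hypertension that is not controlled
- eating disorders
- previous bariatric surgery
- insulin use

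None of these removes the patient in question. The kidney criterion takes out some people who might be more vulnerable, but not the group as a whole.

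**Step 3. Is there another written safeguard?** Neither document mentions medication review, dose adjustment, glucose monitoring, a stopping rule for hypoglycaemia or collection of adverse events. The Design section describes a dietitian consultation but gives it no role in managing medication. Eligibility is therefore the only written protection.

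**Step 4. What is the exposure?** Inputs from the Design section are an 8 h eating window and 8 weeks of diet.

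- Daily fast in the 16:8 arm: 24 - 8 = 16 h.
- Days of intervention: 7 × 8 = 56.
- Excess over a 12 h fast: 16 - 12 = 4 h a day; 4 × 56 = 224 h in total.
- Excess over a 10 h fast: 16 - 10 = 6 h a day; 6 × 56 = 336 h in total.

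The 10 to 12 h range for a usual overnight fast without an eating window is an assumption. The documents do not state one. The Measurements section does mention 12 h ("Blood samples were collected from patients after 12 h of fasting"), but as a sampling condition, not as a patient's habit or a safety limit. The totals also assume full adherence on all 56 days.

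**Step 5. How many patients are exposed?** The documents do not say how many had type 2 diabetes or what drugs they took. The number cannot be derived and may be zero.

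**The case against.** The strongest reply is that no exposed patient has been shown to exist. Diabetes appears in a general definition, everyone qualified through BMI, and nothing records sulfonylurea or glinide use. That is true, and it limits the weight of the point. It does not remove it, because an eligibility rule has to protect patients before anyone knows who will enrol.

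A second reply is that the line was drawn on purpose at the most hazardous drug. The documents neither confirm nor exclude this, and they do not rank the risks. A graded rule would be defensible if the lower-risk group were given dose review or monitoring, but none is described.

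Third, extra fasting hours do not measure hypoglycaemia risk. This stands in full: the 224 to 336 h describe what the schedule asks of a patient, and the conclusion does not depend on them.

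Fourth, silence in so short a protocol is weak evidence that nothing was done. Advice could have been given in consent material, which is not part of the text available here, or in the clinic. That is a fair limit on any claim about conduct. The claim here is only about the rule as written, and an eligibility criterion would not normally sit in a consent form.

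Finally, the hypoglycaemic effect of these drug classes comes from general pharmacology and not from the documents. It is elementary knowledge, and the reply does not dispute it.

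**Conclusion.** The concern holds. As written, the criterion deals with hypoglycaemia risk only in part: it removes insulin users and leaves eligible any patient with type 2 diabetes on another drug that can cause hypoglycaemia, with no compensating safeguard in either document. The energy restriction applies in both arms, so the gap is not confined to the 16:8 arm, although that arm adds the 16 h daily fast.

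The size of the risk cannot be stated, because neither the number of exposed patients nor an event rate is available. The conclusion rests on the text of the eligibility rule and on the general knowledge that sulfonylureas and glinides can cause hypoglycaemia. The change is worth making because it is cheap and applies the Protocol's own stated reason consistently. Nothing here calls the trial's results into question.

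**What to change.** Reword the last exclusion in the Patients section along these lines:

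> Patients on insulin or on other glucose-lowering treatment that carries a risk of hypoglycaemia (e.g. sulfonylureas, glinides), as established from the medication history before randomisation.

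The cost is one changed criterion and a medication check at screening. The Patients section says that a single gastroenterologist conducts the study, so that person could plausibly make the check, although the Protocol does not say who takes the history. The downside is that any patients with type 2 diabetes on these drugs become ineligible, and the results apply slightly less widely.

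If the sponsor prefers to keep such patients, an acceptable alternative is a dose review before the diet starts, with glucose monitoring and reporting of hypoglycaemia. That preserves breadth but takes more work than exclusion.

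The Protocol is written in the past tense. If enrolment is already complete, the rewording can only serve a later version. The sponsor should then report how many patients took such drugs, by arm, and any hypoglycaemia observed.
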